## 4. Study Design

### 4.1. Overall Design

Study I8F-MC-GPHM is a Phase 3, multicenter, randomized, parallel-arm, double-blind placebo-controlled, 84-week study that will investigate the effects of treatment with MTD of tirzepatide (10 mg or 15 mg QW), compared with placebo, on body weight management in study participants who have obesity (BMI  $\geq 30$  kg/m^2) or are overweight (BMI  $\geq 27$  kg/m^2) with at least one weight-related comorbid condition and achieved  $\geq 5.0\%$  weight loss after a 12-week lead-in period with an intensive lifestyle modification program.

Study GPHM will consist of 4 periods: a 2-week screening period; a 12-week lead-in period during which participants undertake an intensive lifestyle modification program to achieve  $\geq 5.0\%$  body weight loss; a 72-week double-blind placebo-controlled treatment period (including a 20-week dose escalation period); and a 4-week safety follow-up period. Study participants who achieve at least 5.0% weight loss will be randomized in a 1:1 ratio (tirzepatide MTD QW or placebo) at the end of the lead-in period. An upper limit of 70% enrollment of women will be used to ensure a sufficiently large sample of men.

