#### Type of Participant and Disease Characteristics

1. Have a BMI of:
  - $\geq 30$  kg/m^2 or
  - $\geq 27$  kg/m^2 and previously diagnosed with at least 1 of the following weight-related comorbidities
    - Hypertension: treated or with systolic blood pressure  $\geq 130$  mmHg or diastolic blood pressure  $\geq 80$  mmHg
    - Dyslipidemia: treated or with low-density lipoprotein (LDL)  $\geq 160$  mg/dL (4.1 mmol/L) or triglycerides  $\geq 150$  mg/dL (1.7 mmol/L), or high-density lipoprotein (HDL)  $< 40$  mg/dL (1.0 mmol/L) for men or HDL  $< 50$  mg/dL (1.3 mmol/L) for women
    - Obstructive sleep apnea
    - Cardiovascular disease (for example, ischemic cardiovascular disease, New York Heart Association [NYHA] Functional Classification Class I-III heart failure)
2. Have a history of at least 1 self-reported unsuccessful dietary effort to lose body weight
3. In the investigator's opinion, are well-motivated, capable, and willing to:
  - learn how to self-inject study drug, as required for this protocol (visually impaired persons who are not able to perform the injections must have the assistance of a sighted individual trained to inject the study drug; persons with physical limitations who are not able to perform the injections must have the assistance of an individual trained to inject the study drug)
  - inject study drug (or receive an injection from a trained individual if visually impaired or with physical limitations)
  - follow study procedures for the duration of the study, including, but not limited to following lifestyle advice (for example, dietary restrictions, exercise plan), maintaining a study diary, and completing required questionnaires

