### 9.4. Statistical Analyses

#### 9.4.1. General Considerations

Statistical analysis of this study will be the responsibility of Lilly or its designee. Any change to the data analysis methods described in the protocol will require an amendment ONLY if it changes a principal feature of the protocol. Any other change to the data analysis methods described in the protocol, and the justification for making the change, will be described in the statistical analysis plan (SAP) or the clinical study report (CSR). Additional exploratory data analyses may be conducted as deemed appropriate.

Unless otherwise noted, all tests of treatment effects will be conducted at a 2-sided alpha level of 0.05, and the confidence interval (CI) will be calculated at 95%, 2-sided. In statistical summaries and analyses, data will be analyzed as randomized.

Unless specified otherwise, efficacy analyses will be conducted using efficacy analysis set (EAS) and safety analyses will be conducted using safety analysis set (SS).

Unless otherwise specified, for analyses in the double-blind period, baseline is defined as the last non-missing data collected prior to or at randomization (prior to first dosing of study drug); for analyses in the lead-in period, baseline is defined as the last non-missing data collected prior to or at study entry (Visit 1 and Visit 2).

Summary statistics for continuous measures will include sample size, mean, SD, median, minimum, and maximum. The analysis model to make comparisons among treatment groups relative to continuous measurements assessed over time will be a mixed model for repeated measures (MMRM), with terms of treatment, visit, treatment-by-visit interaction, stratification factors and baseline measurement as a covariate. An unstructured covariance structure will model relationship of within-patient errors.

Kaplan-Meier method will be used for estimation of cumulative event-free survival rates over time, and cox proportional hazards regression analysis will be used to compare hazard rates among treatments.

Summary statistics for categorical measures (including categorized continuous measures) will include sample size, frequency, and percentages. Logistic regression will be used to examine the treatment difference in binary efficacy outcomes if there is a need to adjust for covariates. Otherwise, Fisher's exact test will be used to examine the treatment difference in categorical outcomes.

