##### **9.4.7.2. Subgroup Analyses for Primary Analysis**

Details of the subgroup analyses will be provided in the SAP.

The following subgroup variables will be considered (but not limited to):

- age (<65 years and  $\geq 65$  years)
- sex (female and male)
- race
- ethnicity
- BMI at study entry (<30,  $\geq 30$  and <35,  $\geq 35$  and <40,  $\geq 40$  kg/m^2)
- percent body weight loss at the end of lead-in (<10% and  $\geq 10\%$ )

The outcome measures for the subgroup analyses will include:

- percent change in body weight from randomization to 72 weeks
- proportion of participants achieving at least 5% body weight reduction from randomization to 72 weeks.

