4. Updated to add body weight at Visit 10 (Week 0) as an additional covariate to the mixed model for repeated measures (MMRM) models for the analyses of mean change in body weight, mean percent change in body weight, and mean change in body mass index (BMI) from Week -12 to Week 72. This covariate adjusts for body weight prior to randomization on the final outcome (see Section [4.4.2.1](#)).
5. Added exploratory endpoints to assess risk difference between tirzepatide maximum tolerated dose (MTD) and placebo arm for an unconditional effect in proportions of participants achieving body weight reduction targets (see Section [4.5](#)).

1. Introduction

Changes to protocol-planned analyses are described in Section [4.9](#).

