4.7.2.1. Subgroup Analysis of Body Weight Change

Subgroup analyses by the following baseline characteristics will be provided:

- age (<65, ≥65 years)
- sex (female and male)
- race
- ethnicity
- BMI at randomization (<30, ≥30 and <35, ≥35 and <40, ≥40 kg/m²)
- region of enrollment (US, outside of US), and
- percentage of body weight reduction at the end of lead-in (<10% and ≥10%).

The outcome measures for the subgroup analyses will include

- percent change in body weight from randomization at 72 weeks, and
- proportion of participants achieving at least 5% body weight reduction from randomization to 72 weeks.

For the percent change in body weight from randomization at 72 weeks, for each subgroup analyses aforementioned, the following analyses will be conducted.

Treatment Regimen Estimand

- Conduct the ANCOVA model on the subgroup only with terms of treatment group, country/pooled country, and sex as fixed effects and baseline body weight as a covariate. Missing body weight measurements at 72 weeks will be imputed using the imputation method described in Section 4.3.2.3.
- Full ANCOVA model - Treatment group, subgroup, treatment-by-subgroup-interaction, country/pooled country, and sex as fixed effects and baseline body weight as a covariate. Missing body weight measurements at 72 weeks will be imputed using the imputation method described in Section 4.3.2.3.

Efficacy Estimand

- Conduct the MMRM model on the subgroup only with terms of treatment group, visit, treatment-by-visit-interaction, country/pooled country, and sex as fixed effects, and baseline body weight as a covariate. The variance-covariance structure for within-patient errors will be same as Section 4.3.2.2.
- Full MMRM model - Treatment group, visit, subgroup, treatment-by-visit-interaction, treatment-by-subgroup-interaction, subgroup-by-visit-interaction, treatment-visit-subgroup-interaction, country/pooled country, and sex as fixed effects and baseline body weight as a covariate. The variance-covariance structure for within-patient errors will be same as Section 4.3.2.2.

For the percentage of participants achieving at least 5% body weight reduction at 72 weeks, for each subgroup analyses aforementioned, the following analyses will be conducted.

Treatment Regimen Estimand

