4.9. Changes to Protocol-Planned Analyses

To provide data on efficacy of the investigational product that would be valuable to better inform clinical decisions in management of people living with obesity, protocol-planned objectives are changed as below.

Key Secondary Objectives

- added the key secondary objective, “QW tirzepatide MTD is superior to placebo for proportion of participants who achieve $\geq 20\%$ body weight reduction from randomization to 72 weeks”

Additional Secondary Objectives

- added the additional secondary objective, “Compare QW tirzepatide MTD with placebo for mean change in Non-HDL-cholesterol (mg/dL) from randomization to 72 weeks”

Subgroup Analysis for Primary Analysis

- added the subgroup variable, “region of enrollment (US, outside of US)” for both outcome measures

5. Sample Size Determination

Approximately 1100 participants will be screened, and 800 participants will be enrolled into the 12-week lead-in period in order to achieve approximately 600 participants randomly assigned to study drug intervention (300 participants per treatment group).

The sample size determination assumes that evaluation of superiority of tirzepatide MTD (10 mg or 15 mg) to placebo will be conducted at a 2-sided significance level of 0.05 using a 2-sample t-test. Additionally, a difference of at least 12% in mean body weight percentage reduction from randomization at 72 weeks for tirzepatide MTD compared to placebo, a common SD of 10%, and a dropout rate of 25% are assumed for statistical power calculations. Under the assumptions above, randomizing 600 participants in a 1:1 ratio to MTD (300 participants) and placebo (300 participants) provides more than 90% power to demonstrate superiority of tirzepatide MTD to placebo.

The chosen sample size and randomization ratio also provides >90% power to establish superiority of tirzepatide MTD to placebo in terms of proportion of participants achieving at least 5% body weight reduction from randomization at 72 weeks, based on a Chi-square test at a 2-sided significance level of 0.05, assuming 20% of placebo-treated participants and 46% of tirzepatide-treated participants achieve the goal and a dropout rate of 25%.

6. Supporting Documentation

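### SAP 4.7.2.1 replaces the protocol's entry-BMI subgroup with BMI at randomization without listing it in 4.9, and no listed subgroup then isolates those enrolled at BMI 27 to below 30

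*SAP*

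**What the plan says.** Protocol 9.4.7.2 introduces its subgroup list with "The following subgroup variables will be considered (but not limited to" and includes "BMI at study entry", cut at 30, 35 and 40 kg/m². It leaves the details to the SAP.

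SAP 4.7.2.1 lists "BMI at randomization" with the same three cut-points. The other variables there are age, sex, race, ethnicity, region and lead-in weight loss (below 10% versus 10% or more). BMI at entry does not appear.

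The SAP introduction tells the reader where departures from the protocol are recorded: "Changes to protocol-planned analyses are described in Section" 4.9. Under its subgroup heading, 4.9 has one entry, the added variable "region of enrollment (US, outside of US". The key changes listed for SAP version 3 do not mention the BMI subgroup either. For changes to analysis methods that need no amendment, protocol 9.4.1 says that the change "and the justification for making the change, will be described in the statistical analysis plan (SAP) or the clinical study report (CSR").

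Two design features bear on this. Inclusion criterion 1 admits people at BMI 30 or above without further condition, and people at BMI 27 or above if "previously diagnosed with at least 1 of the following weight-related comorbidities". Protocol 4.1 then states: "Study participants who achieve at least 5.0% weight loss will be randomized in a 1:1 ratio".

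**The concern.** The cut-points were carried over but the time at which BMI is taken was moved from before the lead-in to after it. Everyone randomized has lost weight in between, so the same labels now describe different people.

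The cut at 30 matters most. At entry it coincides with an eligibility boundary: everyone enrolled below 30 needed a weight-related comorbidity, and nobody at 30 or above did. After the lead-in that correspondence is lost. A reader who takes the SAP's below-30 row as the overweight-with-comorbidity participants would be wrong, and nothing else in the list supplies that comparison. A reader relying on 4.9 would not learn that a subgroup named in the protocol had been dropped.

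**Working it through.** The documents give no figure for this subgroup, so there is none to reproduce. The check compares the passages and then works out how the lead-in shifts the cut-points.

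**Is it a replacement or an addition?** The protocol list has entry BMI and not BMI at randomization. The SAP list has BMI at randomization and not entry BMI. It is a replacement.

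**Inputs.** BMI is weight over height squared (protocol 8.1.2) and height is measured once, at Visit 1 (schedule of activities). BMI therefore falls by the same percentage as weight. The minimum lead-in loss, L, is 5.0% (protocol 4.1). Losses of 10% or more are anticipated, since 10% is a stratification boundary (protocol 6.3). I take entry BMI and lead-in loss from the same starting weight.

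**Formula.** BMI at randomization = entry BMI × (1 − L). A person falls below cut-point c when entry BMI is below c/(1 − L).

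| Cut-point at randomization | Entry BMI limit, 5% loss | Entry BMI limit, 10% loss |
|---|---|---|
| 30 | 30/0.95 = 31.58 | 30/0.90 = 33.33 |
| 35 | 35/0.95 = 36.84 | 35/0.90 = 38.89 |
| 40 | 40/0.95 = 42.11 | 40/0.90 = 44.44 |

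The 5% column is the minimum shift, because nobody randomized has lost less. Everyone entering at 30.0 to just under 31.58 must be in the below-30 class at randomization. Above that it depends on the individual's loss: at entry BMI 33, a 10% loss gives 33 × 0.90 = 29.7 and a 6% loss gives 33 × 0.94 = 31.0. All movement is downward, so the below-30 class keeps everyone enrolled below 30 and gains people enrolled with obesity.

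**How many move?** This needs the distributions of entry BMI and lead-in loss, which the documents do not give. Two sets of assumed inputs show how far the answer depends on them:

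- Entry BMI uniform from 27 to 35 and one common loss for everyone. Of the below-30 class at randomization, the share enrolled at 30 or above is 1.58/(3 + 1.58) = 34% at a 5% loss and 3.33/(3 + 3.33) = 53% at a 10% loss.
- Entry BMI normal with mean 36 to 39 and SD 6 to 7, truncated at 27; loss normal with mean 6 to 9% and SD 1 to 3%, truncated at 5%. By simulation, that share is about 51 to 66%.

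The two ranges barely overlap. Only the limits in the table are fixed by the documents.

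**Size of the entry-BMI stratum.** Under the second set of assumptions, entry BMI below 30 is about 6 to 10% of participants. Of 600 that is 36 to 60 people, or 18 to 30 per arm.

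**The case against.** The case for the SAP's choice is good. SAP 4.7.2.1 calls its list baseline characteristics, and both documents define the double-blind baseline as the last value at or before randomization. Both subgroup outcomes are measured from randomization. BMI at that point is a pre-treatment variable, so comparisons within its classes remain randomized. That it correlates with the lead-in-loss subgroup is ordinary and not a defect. All of this stands.

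The protocol also speaks of variables to be considered, leaves the list open and defers details to the SAP. That readily covers additions. It does not explain why a named variable is gone while 4.9 records a smaller change to the same list. The new variable is stated openly in 4.7.2.1, though, and the clinical study report could still supply the reason. Details of the version 2 changes sit in a version history that is not reproduced, so an entry there cannot be excluded; 4.9 would remain incomplete.

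The Week -12 to Week 0 BMI shift table in SAP 4.5 will show how many enrolled participants change class. It gives no treatment effect by entry BMI, so it helps only in part.

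A reader might infer that the protocol intended this subgroup to test the effect separately in the two eligibility groups. The documents state no such purpose and list four BMI classes. The link is only that the cut at 30 coincides with the eligibility boundary.

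**Conclusion.** The point holds as an unlisted departure from the protocol that loses one named subgroup analysis. The SAP's below-30 class must include everyone who entered at BMI 30.0 to just under 31.58, and takes in people up to 33.3 at a 10% loss. It therefore does not correspond to those enrolled at BMI 27 to below 30 with a comorbidity, and no other listed subgroup does. This rests only on the 5.0% randomization requirement and on entry BMI and loss sharing a starting weight.

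Three stronger readings are tempting and unsupported. The subgroup results are not biased. The primary test, alpha and power are not touched. No particular share of reclassified participants can be asserted, because every such figure depends on assumed distributions. The consequence is confined to interpreting one subgroup and to the completeness of 4.9, so the matter is minor.

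**What to change.** In SAP 4.7.2.1, add BMI at study entry (below 30, 30 to below 35, 35 to below 40, and 40 kg/m² or above) for both co-primary outcomes, and keep BMI at randomization as an additional subgroup. In SAP 4.9, list the change to the BMI subgroups with its reason.

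The data are already collected: height and weight at Visit 1, and weight again at Visit 2. The cost is some SAP wording and one extra forest-plot row. The entry-BMI stratum below 30 may be small, so its estimate may be imprecise and the subgroup-only models with country and sex terms may be unstable there. The row should be read with that in mind.

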4.8. Interim Analyses

Not applicable.

4.9. Changes to Protocol-Planned Analyses

To provide data on efficacy of the investigational product that would be valuable to better inform clinical decisions in management of people living with obesity, protocol-planned objectives are changed as below.

Key Secondary Objectives

- added the key secondary objective, “QW tirzepatide MTD is superior to placebo for proportion of participants who achieve $\geq 20\%$ body weight reduction from randomization to 72 weeks”

Additional Secondary Objectives

- added the additional secondary objective, “Compare QW tirzepatide MTD with placebo for mean change in Non-HDL-cholesterol (mg/dL) from randomization to 72 weeks”

Subgroup Analysis for Primary Analysis

- added the subgroup variable, “region of enrollment (US, outside of US)” for both outcome measures

5. Sample Size Determination

Approximately 1100 participants will be screened, and 800 participants will be enrolled into the 12-week lead-in period in order to achieve approximately 600 participants randomly assigned to study drug intervention (300 participants per treatment group).

The sample size determination assumes that evaluation of superiority of tirzepatide MTD (10 mg or 15 mg) to placebo will be conducted at a 2-sided significance level of 0.05 using a 2-sample t-test. Additionally, a difference of at least 12% in mean body weight percentage reduction from randomization at 72 weeks for tirzepatide MTD compared to placebo, a common SD of 10%, and a dropout rate of 25% are assumed for statistical power calculations. Under the assumptions above, randomizing 600 participants in a 1:1 ratio to MTD (300 participants) and placebo (300 participants) provides more than 90% power to demonstrate superiority of tirzepatide MTD to placebo.

The chosen sample size and randomization ratio also provides >90% power to establish superiority of tirzepatide MTD to placebo in terms of proportion of participants achieving at least 5% body weight reduction from randomization at 72 weeks, based on a Chi-square test at a 2-sided significance level of 0.05, assuming 20% of placebo-treated participants and 46% of tirzepatide-treated participants achieve the goal and a dropout rate of 25%.

6. Supporting Documentation

6.1. Appendix 1: Demographic and Baseline Characteristics

6.1.1. Patient Characteristics

A listing of participant demographics for all randomized participants will be provided. All demographic and baseline clinical characteristics will be summarized by study treatment for all randomized participants. Baseline demographic and clinical characteristics of special interest include but are not limited to age (years), sex (female, male), race, ethnicity, height (cm), weight (kg), BMI (kg/m²), waist circumference (cm), age group (<65 years, ≥65 years), BMI group (<30, ≥30 and <35, ≥35 and <40, ≥40 kg/m²), country, and weight-related comorbidities.

6.1.2. Historical Illnesses and Preexisting Conditions

The count and percentages of participants with historical illnesses and preexisting conditions will be summarized by treatment group using MedDRA PTs nested within SOC. The SOCs will be in alphabetical order. Conditions (that is, PTs) will be ordered by decreasing frequency within SOC. This will be summarized for all randomized participants.

6.1.3. Concomitant Therapy

Concomitant medications will be summarized by PTs by treatment group by decreasing frequency for the SS group. The following postbaseline period will be considered:

- up to 72 weeks plus the safety follow-up (Visit 801) for all randomized participants.

Additionally, concomitant medications of interest (as defined below) will be summarized by treatment for the SS.

Concomitant medications of interest include the following:

- baseline antihypertensive therapy, by type/class
- baseline lipid lowering therapy, by type/class
- changes to baseline medication postrandomization
 - antihypertensive therapy, and
 - lipid lowering therapy.
- utilization after randomization of
 - medicines that cause weight gain,
 - antihyperglycemic medication for the treatment of diabetes for participants who develop T2DM during the study (antihyperglycemic medication for the treatment of prediabetes is not allowed per protocol)
 - antidiarrheal medication, and
 - antiemetic medication.

The analysis of concomitant medication for the lead-in period is provided in Appendix 4 (Section 6.4).

6.2. Appendix 2: Treatment Compliance

A summary of participants who prematurely discontinued study treatment (including discontinuation reason) will be provided by study treatment. A time-to-event analysis of premature study treatment discontinuation will also be conducted.

The analyses related to compliance during the 72-week treatment period will be conducted for all randomized participants.

If data warrant, the counts and percentages of participants who follow the planned escalation scheme, have dose interruption, or have dose de-escalation/re-escalation will be summarized for the tirzepatide treatment group. In addition, the proportion of participants receiving 2.5 mg, 5 mg, 7.5 mg, 10 mg, 12.5 mg, or 15 mg may be presented by visit during the dose escalation period.

Treatment compliance will be defined as taking at least 75% of the scheduled study treatment doses. Compliance over the double-blind treatment period will be calculated using the number of doses administered (regardless of the actual dose in mg administered), divided by the total number of doses expected to be administered $\times 100$ over the double-blind treatment period, respectively. Treatment compliance will be summarized descriptively over the double-blind treatment period by treatment using the mITT population.

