### ***End of Visit 10 to Visit 28***

During the treatment period, office visits will occur as indicated in the SoA (Section 1.3). Telephone visits will occur at 4-week intervals between the office visits starting at Visit 17.

Office visit procedures should be conducted according to the SoA (Section 1.3), and will include

- weight, waist circumference and vital signs measurements
- laboratory testing
- administration of PRO questionnaires
- collection of AEs, product complaints and concomitant medications
- Mental Health questionnaires
- review of participant diary information (to include reinforcement and compliance assessments for study drug administration and lifestyle goals)
- drug dispensing.

Patient-reported outcomes questionnaires should be administered as early as possible, as per Suggested Visit Structure (Section 10.8). Preferred administration order is the same as Visit 2.

Mental Health questionnaires should be completed after the assessment of AEs.

Dietician consultations occur every 12 weeks from Week 0 to Week 72. Study drug and injection supplies will be returned per the SoA (Section 1.3) and according to local requirements. New supplies will be dispensed as needed.

The starting dose of tirzepatide is 2.5 mg QW (or matching placebo) for 4 weeks, then the dose is increased by 2.5 mg (or matching placebo) every 4 weeks (2.5 to 5 to 7.5 to 10 to 12.5 to 15 mg) up to MTD (either 10 mg or 15 mg).

Interventions to optimize study drug tolerance and adherence may be employed throughout the study and include, but are not limited to, brief temporary interruptions and use of additional medications to manage GI symptoms (for example, nausea, vomiting, and diarrhea, see Section 6.6.2. for details).

During the first 24 weeks of the treatment period (20-week dose escalation plus 4 weeks), participants unable to tolerate 2.5 mg or 5 mg despite the above measures will be discontinued from the study drug but remain in the study for continued follow up. For participants unable to tolerate any dose escalation between 7.5 mg and 15 mg inclusive, despite the above measures, the investigator should contact Lilly to consider a dose de-escalation step with subsequent re-escalation in a blinded fashion to reach either the 10-mg or 15-mg dose as described below (only 1 cycle of dose de-escalation and re-escalation is permitted during the first 24 weeks of the treatment period):

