## 6.3. Measures to Minimize Bias: Randomization and Blinding

This is a double-blind, randomized study.

Participants who meet all criteria for enrollment will undergo a 12-week intensive lifestyle modification lead-in period. Those who achieve  $\geq 5.0\%$  weight loss at Visit 10 will be randomized to one of the study treatment groups (tirzepatide MTD or placebo) for the duration of the treatment period. Assignment to treatment groups will be determined by a computer-generated random sequence using an IWRS. Participants will be randomized in a 1:1 ratio to receive tirzepatide MTD or placebo.

The randomization will be stratified by country, sex (female, male), and percent weight loss at the end of lead-in ( $<10\%$  versus  $\geq 10\%$ ).

Investigators, site staff, clinical monitors and participants will remain blinded to the treatment assignments until the study is complete.

Emergency unblinding for AEs may be performed through the IWRS. This option may be used ONLY if the participant's well-being requires knowledge of the participant's treatment assignment. All emergency unblinding events are recorded and reported by the IWRS.

If an investigator, site personnel performing assessments, or participant is unblinded, the participant must be discontinued from the study. In cases where there are ethical reasons to have the participant remain in the study the investigator must obtain specific approval from a Lilly clinical research physician (CRP) for the participant to continue in the study.

In case of an emergency, the investigator has the sole responsibility for determining if unblinding of a participant's treatment assignment is warranted for medical management of the event. The participant's safety must always be the first consideration in making such a determination. If a participant's treatment assignment is unblinded, Lilly must be notified immediately. If the investigator decides that unblinding is warranted, it is the responsibility of the investigator to promptly document the decision and rationale and notify Lilly as soon as possible.

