### 7.1.1. Temporary Discontinuation

In certain situations, after randomization, the investigator may need to temporarily interrupt study drug. Every effort should be made by the investigator to maintain participants on study drug and to restart study drug after any temporary interruption, as soon as it is safe to do so. Distribution of study drug at the correct dose will be per IWRS instructions.

If study drug interruption is...	then...
2 consecutive doses or less	participant restarts study drug at last administered dose, as per escalation schedule.
3 consecutive doses or more	participant restarts study drug at 5 mg (managed by IWRS) and repeats dose escalation scheme.
due to an AE	the event is to be documented and followed according to the procedures in Section 8.3 of this protocol.
due to intolerable persistent GI AE	participants should be treated as suggested in Section 6.6.2.

Investigators should inform the sponsor that study drug has been temporarily interrupted. The data related to temporary interruption of study treatment will be documented in source documents and entered on the eCRF.

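### SAP 6.2 plans the summary of escalation adherence, dose interruption and de-escalation/re-escalation for tirzepatide only, so these rates have no prespecified placebo comparator

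*SAP*

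**What the plan says.** SAP 6.2 introduces the summary conditionally: "If data warrant, the counts and percentages of participants who follow the planned escalation scheme". The same sentence adds those who "have dose interruption, or have dose de-escalation/re-escalation will be summarized for the tirzepatide treatment group". The sentence just before it says that compliance analyses over the 72 weeks cover everyone randomised. The same appendix presents premature treatment discontinuation (with reason) and compliance by treatment.

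The protocol applies the dosing steps to both arms:

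- **Escalation** (4.1.1.2.3): after the starting step, "then the dose is increased by 2.5 mg (or matching placebo) every 4 weeks".
- **De-escalation** (4.1.1.2.3): for participants who cannot tolerate a step from 7.5 mg upward, the investigator contacts the sponsor to "consider a dose de-escalation step with subsequent re-escalation in a blinded fashion". The rule names no arm.
- **Interruption** (7.1.1): after three or more consecutive missed doses, the "participant restarts study drug at 5 mg (managed by IWRS) and repeats dose escalation scheme". On recording: "The data related to temporary interruption of study treatment will be documented in source documents and entered on the eCRF".
- **Blinding** (6.3): "Investigators, site staff, clinical monitors and participants will remain blinded to the treatment assignments until the study is complete".

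**The concern.** Dose interruptions are not all caused by the drug. Protocol 7.1.1 allows them for any adverse event, and Protocol Appendix 10 foresees supply problems in exceptional circumstances. Background gastrointestinal symptoms can also lead to an interruption or a de-escalation step in a blinded trial. A percentage from the tirzepatide arm alone therefore mixes drug effect with background, and the planned table gives the reader no way to separate the two.

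This matters because the treatment under study is a maximum tolerated dose reached through this scheme. The share of participants who follow it as planned, interrupt dosing or need a de-escalation cycle describes directly how the scheme was tolerated. A blinded, randomised control group goes through the same scheme, yet the SAP leaves it out of this summary. What is at stake is how well a descriptive table can be interpreted, not a test result.

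**Working it through.** The documents give no expected rate of interruption or de-escalation, so there is no plan figure to reproduce. The check is mainly textual.

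**1. Is the restriction real?** Yes. The specific sentence in SAP 6.2 names the tirzepatide group only. The general sentence before it, covering all randomised participants, is in tension with it. Read in the ordinary way, the specific sentence governs.

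**2. Does placebo go through the same steps?** Yes. Protocol 4.1.1.2.3 gives matching placebo at each escalation step and makes de-escalation blinded. Protocol 6.6.2 allows a one-dose interruption of study drug for gastrointestinal symptoms, whichever the arm. Protocol 7.1.1 manages restarts through the IWRS. Sites and participants are blinded, so they cannot apply these rules to one arm only.

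**3. Does another SAP output give these rates by arm?** No.

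| SAP output | By treatment? | Shows interruption or de-escalation? |
|---|---|---|
| Premature discontinuation with reason (4.2, 6.2) | Yes | No, permanent stops only |
| Nausea, vomiting, diarrhea; severe GI events (4.6.5.2) | Yes | No, symptoms only |
| Antiemetic and antidiarrheal use (6.1.3) | Yes | No, medication only |
| Compliance of at least 75% of doses (6.2) | Yes | Hardly; see step 4 |
| Listing of interruptions from exceptional circumstances (6.6.2) | Optional listing | No rates, and this cause only |

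**4. Could by-treatment compliance stand in?** SAP 6.2 defines compliance as doses administered / doses expected × 100 over the double-blind period, whatever the mg strength. Weekly dosing for 72 weeks gives about 72 expected doses.

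- One-dose interruption: 71/72 = 98.6%.
- Three consecutive missed doses, enough to trigger a restart at 5 mg: 69/72 = 95.8%.
- Threshold reached: 54/72 = 75.0%, which is 18 missed doses.
- De-escalation with no dose missed: 72/72 = 100%.

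All four participants count as compliant. The measure cannot show a de-escalation and registers interruptions only when many doses are lost.

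**5. Coverage.** With 1:1 allocation of about 600 participants, the planned summary covers about 300 and leaves out about 300.

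**The case against.** The strongest reply is that this is an optional description of dosing in the only arm that receives a mg dose. Protocol 6.1 lists the placebo dose as not applicable. The summary carries no test, sits in a compliance appendix rather than in the safety section, and feeds no objective or endpoint. Controlled evidence on tolerability is already planned through discontinuation, adverse events, GI events and symptomatic medication. Participants who cannot reach 10 mg after one de-escalation attempt are taken off study drug, so outright failure of the scheme does reach the by-treatment discontinuation analysis. Protocol 9.4.2.4 also plans compliance by arm and visit.

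Most of this stands and sets the weight of the point. It does not remove it. Participants who interrupt and resume, who re-escalate successfully, or who settle on 10 mg after a de-escalation cycle do not appear in the discontinuation analysis. By-visit compliance would help a little. However, one missed dose in a four-week interval is 3/4 = 75% and still counts as compliant, and de-escalation remains invisible. The argument about mg dose justifies keeping the by-visit dose-level table to tirzepatide. It does not extend to interruptions or to blinded steps that placebo participants also take.

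A reader might infer that the trial cannot say how much of the interruption or de-escalation is drug-related. The documents do not support that. Interruptions are recorded on the eCRF without distinction by arm, and SAP 4.1 permits additional analyses, so the comparison can be made. It is only not prespecified. Nor does a labelled one-arm count in itself attribute every event to the drug.

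**Conclusion.** The point holds and is minor: a free improvement. Escalation adherence, dose interruption and de-escalation/re-escalation are planned for one arm, although both arms undergo them under blinding, and no other SAP output supplies the placebo rates. Alpha, power, and primary and key secondary inference are unaffected.

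The numerical effect of adding placebo cannot be estimated from the documents, because neither gives an expected rate in either arm. The conclusion rests on two readings. The first is that the specific tirzepatide-only sentence overrides the general one before it. The second is that placebo de-escalation steps can be recovered from IWRS or eCRF records. For interruptions, eCRF capture is stated in Protocol 7.1.1. For de-escalation steps it is a reasonable inference from blinded, IWRS-managed dispensing, but it is not stated.

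**What to change.** In SAP 6.2, replace the restriction to the tirzepatide arm with *by treatment group* for all three items: following the planned escalation, any dose interruption, and any de-escalation/re-escalation. State that placebo steps are counted at the matching dose level, taken from IWRS and eCRF records. This also removes the tension with the preceding sentence. Between-arm differences with 95% confidence intervals may be added for interruption and for de-escalation/re-escalation, but are not essential. Leave the by-visit table of mg dose received for tirzepatide only.

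The cost is one phrase in the SAP and one more column in a planned table, plus a little programming if the intervals are added. No protocol amendment and no change to any dosing rule is needed. Interruptions need no new data. For de-escalation, confirm before database lock that the step history is available for both arms.
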